Aim 2 is about unseating one of these modular networks with a perturbation and showing that the reorganization of these networks can be understood from the cascade-like interactivity across the body. Healthy adults will maintain an upright stance on an unstable surfacea balance boardin one condition and perform the Trail Making Test while maintaining an upright stance on the same unstable surface in the other. We hypothesize that destabilizing contact with the ground surface when maintaining an upright stance will produce modular networks of multiplicative interactions with increased connectivity among these modules compared to stable standing (Hypothesis 2.1). We hypothesize that destabilizing contact with the ground surface when taking part in the Trail Making Test would produce a succession of distinct, modular networks of multiplicative interactions with increased connectivity among these modules compared to stable standing (Hypothesis 2.2).

Since fewer modular networks typically exhibit sparser intra-modular and denser inter-modular connections, we expect an inverse correlation between modularity and between-module connectivity from a theoretical standpoint.

CHARACTERISTICS OF THE SUBJECT POPULATION

4. Accrual

A. Is this study conducted solely at sites under the oversight of the UNMC IRB (e.g. UNMC, Nebraska Medicine, CHMC, UNO)?

Yes

1. How many subjects will need to be consented (per group, as applicable) in order to achieve the scientific objectives of the research?

50 healthy adults; 25 men and 25 women

2. What is the statistical or other justification for the total number of subjects described above?

Sample size determination was made based on previously observed values of statistical descriptors of movement variability in older and younger adults (older: $H = 0.64 \pm 0.08$; younger: 0.76 ± 0.07 (Hunt et al., 2014; Kaipust et al., 2013; Raffalt et al., 2021; Vaz et al., 2019; Vaz et al., 2020) and the procedure outlined in Kuznetsov and Rhea (2017). The method entails generating simulated datasets with known parameters. Power Analysis conducted across 1000 simulated datasets revealed that 16 participants per group will yield 86%, 94%, and 100% power to detect a difference of 0.1, 0.05, and 0.3 in H for fixed effects of Sex and the two nestings of experimental manipulation. We will recruit $N = 25$ participants per age group to account for possible attrition, equipment failures, etc.

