3. How long do you estimate it will take to accrue the required number of subjects?

We will take about 60 weeks = 15 months at the rate on one participant per week, including 10 week for vacations etc.

5. Gender of the Subjects

A. Are there any enrollment restrictions based on gender?

No

6. Age Range of Subjects

A. Will adults be enrolled ?

Yes

1. What is the age range of the adult subjects?

19 to 35 years old healthy young adults will participate (a separate study will be planned to include middle age and older adults). Since the proposed project has a within-subjects design, each participant will be subjected to each experimental condition.

2. What is the rationale for selecting this age range?

Our choice of 19 to 35 years old participants is based on two reasons: (i) the movement system starts to show slowing and deterioration in most adults as they reach 40 years of age; and (ii) we plan a future study with comparisons to middle-aged and older adults to study how the movement system deteriorates with age.

B. Will children (18 years of age or younger) be included in this research?

No

1. What is the justification for excluding children from participating in this research?

♦ Research is irrelevant to children (e.g. disease or condition rarely encountered in children).

Knowledge being sought in the research is already available for children or will be obtained from another ongoing study.

A separate study in children is warranted and preferable.

Insufficient data are available in adults to judge the potential risk in children.

Other. Explain.

7. Race and Ethnicity

Are there any subject enrollment restrictions based upon race or ethnic origin?

No

8. Vulnerable Subjects

A. Will prisoners be included in the research?

No

B. Select from the list all of the vulnerable populations that will specifically be recruited to participate in this research.

Decisionally-impaired persons

Critically ill patients

Students of the investigator

Employees of the investigator

Educationally disadvantaged individuals

Socially or economically disadvantaged individuals

Individuals with a stigmatizing illness or condition

Individuals from a marginalized social or ethnic group
Other.

- ◆ No vulnerable subjects will be specifically recruited

9. Inclusion Criteria

What are the specific inclusion criteria?

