C. Are breast feeding women excluded in this research?

No

Provide justification for the inclusion or exclusion of breast feeding women.

There is no added danger to breast feeding women during sighted or blindfolded walking sessions in this protocol.

METHODS AND PROCEDURES (NON-THERAPEUTIC)

12. Methods and Procedures Applied to Human Subjects

A. Describe the research plan, including all procedures, interventions, evaluations and tests. If subjects will be randomized to a specific intervention, the randomization plan should be explained.

Tasks, procedure, and instructions to the participant

Participants will be tested in an indoor laboratory in the Biomechanics Research Building at the University of Nebraska at Omaha. After taking informed consent, participants will be fitted with retroreflective markers and an eye tracker (see below). In Aim 1, participants will maintain an upright stance on a stable surface a pair of force plates in one condition and perform the Trail Making Test while maintaining an upright stance in the other. The Trail Making Task will be presented on a projector screen and involve drawing a trail through jumbled numbers. In Aim 2, participants will maintain an upright stance on an unstable

surface a balance board placed on the force plates in one condition and perform the Trail Making Test while maintaining an upright stance on the same unstable surface in the other. Each trial is expected to last about seven-eight minutes and will be repeated if the participants lost balance at any time between the trial for a maximum of two repetitions. Participants will be subjected to three trials of each of the four conditions in a single experimental session lasting 120 mins. The order of the 12 trials will be randomized for each participant.

Balance board

Balance boards, which include rocker boards and wobble boards, are a fitness tool people can stand on while performing exercises to help improve balance and posture, aid in rehabilitation, prevent lower body injuries, and increase core strength, among other benefits. We will use a lateral balance board as show in the attached picture.

Posturography

Participants will stand on dual 40×60 cm floor-embedded force plates (400600HPS, AMTI Inc., Watertown, MA) with one foot on each force plate. Participants will be given no additional instructions that can impose artificial constraints on the posture. Ground reaction forces will be recorded at 200 Hz.

Motion tracking

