What are the potential risks associated with each research procedure, intervention, evaluation and/or test? If data are available, estimate the probability that a given harm may occur and its potential reversibility.

The potential risks of standing are similar to general bouts of light physical activity, the most likely one being fatigue due to extended standing. The trials in which participants will be asked to maintain balance on a balance board run the risk of losing balance. Balancing on the balance board might pose additional risk of loosing balance and falling. We will cover all surface adjacent to the participant with thick styrofoam to prevent injury in the unlikely case of fall.

17. Risk Classification

What is the overall risk classification of the research?

- ◆ Minimal risk

Greater than minimal risk

18. Minimization of Risk

A. Describe how the subjects of the research will be monitored by the investigators and other research personnel to ensure their safety.

We will cover all surfaces adjacent to the participant with thick styrofoam to prevent injury in

the unlikely case of a fall when balancing on the balance board. Also, the study will be terminated if the participant report to have any kind of loss of balance while participating in the study.

B. Describe how the data collected will be monitored to ensure the safety of subjects. Identify who will perform the ongoing data and safety analysis, and describe the frequency of data analysis. If there is an independent Data and Safety Monitoring Board (DSMB) provide the charter, or describe (1) the composition of the DSMB membership, (2) the frequency of DSMB meetings and reports.

Collected data will be temporarily stored on an encrypted, password-protected local hard drive after data collection sessions have been completed. After being uploaded to a secure UNO Office365 server that only the listed personnel will have access to, they will be removed from the local hard drive. Hard paper copies will be stored in a lockable file cabinet within a locked room only accessible to the listed personnel. The PI will perform ongoing data and safety analysis. Data monitoring by the PI will occur every month.

C. Describe the auditing plan for research conducted. Identify who will conduct the audits and specify the audit frequency.

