The primary investigator will be in charge of auditing the research (every 2 months) if discrepancies are found between the data collection, analysis, or logging procedures.

D. Describe the specific subject withdrawal criteria.

Participants will be asked throughout the data collection period if they are experiencing any physical discomfort and will be withdrawn from the study if stated that they do experience any physical discomfort. If the subject appears to be off balance or unsteady, they will be withdrawn from the study. Participants only need to express this to an investigator if they desire to withdraw. Suppose any aspect of the research negatively impacts their health or they no longer fit the eligibility criteria at any point in the research. In that case, the participant will be taken off the study. The study does not have any treatment or intervention beyond minimal physical activity. Therefore there is no consequence to the participant for withdrawing from the protocol

E. Describe the stopping rules for the research (e.g., the specific criteria for halting or early termination of the study).

The data collection sessions will be halted for reasons including, but not limited to: injury of any kind during data collection, equipment malfunction that may put the participants in increased harm, signs of physical injury, or expression of physical discomfort. We do not expect participants falling to be common during this project. However, if any participants fall, the study session will be terminated.

F. Describe plans and resources available to promptly address any subject injury.

The Biomechanics Research Building and the Health & Kinesiology Building have Emergency Action Plans that all investigators are familiar with. The procedures are listed in the attached document.

19. Potential Benefits to the Subject

Is there the prospect for direct benefit (eg, research on diagnosis or treatment of disease)?

No

20. Potential Benefits to Society

Describe the potential benefits to society that may reasonably be expected to result from this research.

The knowledge generated by this project will lay the foundations of a new way to understand suprapostural dexterity and its breakdown in various movement disorders.

FINANCIAL OBLIGATIONS AND COMPENSATION

22. Financial Obligations of the Subject

A. Who will pay for research procedures, interventions, evaluations and tests? Check all that apply.

Sponsor

Grant

CRC, CCTR

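### Loss of balance leads to a repeated trial in one section and to exit in two others; separately, blocking the trial order would be a cheap safeguard

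*Protocol*

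**What the plan says.** Handling of a loss of balance appears in four places in the protocol.

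- Section 12.A (tasks and procedure): a trial "will be repeated if the participants lost balance at any time between the trial for a maximum of two repetitions".
- Section 18.A (safety monitoring): "the study will be terminated if the participant report to have any kind of loss of balance while participating in the study".
- Section 18.D (withdrawal criteria): "If the subject appears to be off balance or unsteady, they will be withdrawn from the study".
- Section 18.E (stopping rules): a fall ends the session, with the remark "We do not expect participants falling to be common during this project".

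On the layout of the session, 12.A states "Participants will be subjected to three trials of each of the four conditions in a single experimental session lasting 120 mins", and then "The order of the 12 trials will be randomized for each participant". Two of the four conditions use a balance board. Section 6.A.1 gives the premise: "Since the proposed project has a within-subjects design, each participant will be subjected to each experimental condition". Section 4.A.2 sets 16 per group as the number needed and recruits 25 "participants per age group to account for possible attrition, equipment failures, etc".

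**The concern.** The first issue is a contradiction. Aim 2 stands people on a board chosen to destabilise them, so loss of balance and visible unsteadiness are foreseeable in half of the trials. Staff following 12.A would run the trial again and keep the participant. Staff following 18.A or 18.D would end that person's participation.

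The two courses give different datasets. Under the first, some board trials are second or third attempts, made with more practice and more fatigue. Under the second, the board data come mainly from people who kept their balance, and others leave with some trials not done. If staff choose case by case, the data are an undocumented mixture. None of this can be repaired after collection.

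The second issue follows from the first. Sessions may end early, and the analysis compares conditions within a person. The order of trials then decides whether a shortened session still holds all four conditions.

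**Working it through.** **1. The passages side by side**

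| Event | 12.A | 18.A | 18.D | 18.E |
|---|---|---|---|---|
| Loss of balance that the participant reports | repeat | terminate | withdraw, if visible | not addressed |
| Loss of balance seen by staff, not reported | repeat | not addressed | withdraw | not addressed |
| Fall | repeat, read literally | terminate, if reported | withdraw | end session |

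A loss of balance can trigger a repeat only if someone notices it. If the participant reports it, 18.A applies. If staff see it, 18.D applies. So every event that starts a repeat under 12.A also meets an exit rule, and nothing is left to which the repeat rule alone applies.

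**2. Order of trials: inputs**

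From 12.A: 4 conditions × 3 trials = 12 trials, which reproduces the plan's count. The order is random per participant with no stated restriction, so a plain shuffle is the natural reading. In a plain shuffle every condition has the same expected position, so the order does not bias condition comparisons in complete sessions.

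**3. Is a condition missing after k completed trials?**

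For a plain shuffle, by inclusion-exclusion:

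P(all four seen) = [C(12,k) − 4·C(9,k) + 6·C(6,k) − 4·C(3,k)] / C(12,k)

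| k | Numerator | C(12,k) | Condition missing, shuffle | Condition missing, three blocks of four |
|---|---|---|---|---|
| 4 | 495 − 504 + 90 = 81 | 495 | 83.6% | 0% |
| 5 | 792 − 504 + 36 = 324 | 792 | 59.1% | 0% |
| 6 | 924 − 336 + 6 = 594 | 924 | 35.7% | 0% |
| 7 | 792 − 144 = 648 | 792 | 18.2% | 0% |
| 8 | 495 − 36 = 459 | 495 | 7.3% | 0% |
| 9 | 220 − 4 = 216 | 220 | 1.8% | 0% |

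With three or fewer completed trials neither scheme holds all four conditions. With ten or more both always do.

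**4. What that means for 50 participants**

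The protocol gives no stop rate. Assume that the first loss of balance ends the session, that it occurs with chance p on each board trial only, and that the trial in which it occurs is lost. Let b be the number of board trials up to and including the first trial of the last condition to appear. The chance of lacking a condition is 1 − mean[(1−p)^b]. When blocked, b is always 2. For the shuffle the mean is taken over all 369,600 orders.

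| p (assumed) | Sessions stopped, 50·[1−(1−p)^6] | Lacking a condition, shuffle | Lacking a condition, blocked | Gain |
|---|---|---|---|---|
| 1% | 2.9 | 50 × 0.0299 = 1.5 | 50 × 0.0199 = 1.0 | 0.5 |
| 2% | 5.7 | 50 × 0.0592 = 3.0 | 50 × 0.0396 = 2.0 | 1.0 |
| 5% | 13.2 | 50 × 0.1427 = 7.1 | 50 × 0.0975 = 4.9 | 2.3 |

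A simulation of the same model gave 0.5, 1.0 and 2.4.

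Allowance for attrition: if the groups in 4.A.2 are the 25 men and 25 women (an assumption, since the text there speaks of age groups), 50 − 2 × 16 = 18 can be lost. Expected losses stay below 18 under either order.

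**5. Cost in changes of surface**

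Shuffle: 11 adjacent pairs × 6/11 = 6 changes between board and no board. Blocked: 3 blocks × 3 pairs × 2/3 = 6, plus 2 joins between blocks × 1/2 = 1, so 7 in all.

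**The case against.** On the contradiction, one can argue that the sections describe different degrees of event: a brief loss of balance leads to a repeat, and a fall or real unsteadiness to an exit. That may be what was meant. But 18.A covers a loss of balance of any kind, and 18.D sets no degree of unsteadiness, so the text does not draw that line.

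On the order, the case against is strong and much of it stands. The stated scheme is valid, and the protocol neither describes nor excludes blocking. The participant counts rest on assumed rates and on one side of the unresolved conflict: if 12.A governs, many of the modelled stops become repeats and most of the gain goes. If partial sessions are not analysed, there is no gain at all. The percentages by number of completed trials apply only to sessions that stop at exactly that point; they are not a risk to the study as a whole. What remains is that blocking needs no extra trials or participants and cannot be added later.

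Two stronger readings are tempting and not supported.

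- A reader might infer that the shuffle is an error or threatens power. It is unbiased, and expected losses stay within the allowance at the rates shown.
- A reader might infer that the permitted repeats cannot fit into 120 minutes. The maximum of two could be a session total, and 14 × 8 = 112 minutes fits. Even per trial it is a ceiling, not an expected load. Elsewhere the protocol allows up to three hours (11.B.3) and gives a pay example of two hours fifteen minutes (23.A.1).

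**Conclusion.** The handling of loss of balance is wrong as written: 12.A conflicts with 18.A and 18.D for the same event. This rests on the text alone. It has no numerical size, because no frequency is documented, but it bears on who stays in the study and on which board trials exist for Aim 2. This review takes no position on which rule should apply.

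Blocking the order is a cheap improvement and not the correction of an error. Its benefit is confined to sessions that stop after four to nine completed trials. It amounts to about 0.5 to 2.3 of 50 participants if a loss of balance ends the session at 1% to 5% per board trial, and it requires that completed trials from stopped sessions be analysed. If stops come mainly from board trials, missing data will depend on condition and on the person's stability; neither order removes that.

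**What to change.** Reconcile 12.A, 18.A and 18.D, and check 18.E against them, so that each kind of balance event has one stated consequence. Which consequence is for the investigator and the ethics board to decide. The cost is a change of wording.

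Optionally, state in 12.A that the 12 trials are randomised in three blocks, each holding the four conditions once in random order; if the list is already built this way, say so. Include block or trial position in the condition comparison, and state whether completed trials from stopped sessions are analysed. The cost is a different list, one model term and one sentence, with about one more change of surface per session (7 instead of 6). The next condition also becomes slightly more predictable, which matters little because participants know which condition they are in.

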A series of recent studies have modeled postural stability as a modular structure of functional networks shaped by the anatomical constraints of the musculoskeletal system (Boonstra et al., 2016, 2015; Esteve-Altava et al., 2015; Kerkman et al., 2020, 2018; Murphy et al., 2018). This arrangement indicates a soft assembly and disassembly of functional modules as an individual engages in a task and responds to changing task demands, respectively. However, critically, movement science follows the prevailing tradition in network approaches of preserving spatial or structural information while collapsing across time (Bartsch et al., 2015; Bashan et al., 2012; Gosak et al., 2022; Ivanov et al., 2016; Rizzo et al., 2020). Collapsing variability across time leads to the lack of generalizability of results because variability is not the same across space and time. In contrast, cascades carry information about uncollapsed time, the texture, and the variation that dexterous posture will

have as the body coordinates longer timescale factors like intention for task completion with shorter-timescale factors like perturbations and corrective movements. Cascade modeling allows us to articulate how seemingly differentiated forms can arise from fluid interactions of the movement-system components across many timescales (Kelty-Stephen et al., 2022, 2013; Kelty-Stephen and Mangalam, 2022b). Cascades operate through the loose nesting of finer motoric details within larger motoric degrees of freedom (e.g., motor neurons within bundles of muscle fiber, muscles within joint-centered synergies, and so on) that allow dexterous behavior to adapt flexibly to constraints changing on the way to task completion. We have previously shown this capacity for cascades to knit events across many timescales is similar in postural sway, no matter whether we load the upper body (Furmanek et al., 2020; Kelty-Stephen et al., 2020), destabilize contact with the ground surface (Kelty-Stephen, 2018; Mangalam and Kelty-Stephen, 2021), or increase visual effort (Mangalam et al., 2021). However, treatment could be tailored and targeted if we know what specific network structures support suprapostural dexterity and how these networks assemble and dissemble.

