such as cognitive flexibility, alternating attention, sequencing, visual search, and motor speed, among other functions (Bowie and Harvey, 2006; Reitan, 1958; Sanchez-Cubillo et al., 2009). Performing the Train Making Task must introduce longer-timescale constraints on the postural system already satisfying the shorter-timescale demands of postural stability. It is expected that the culmination of shorter-timescale postural constraints and longer-timescale constraints imposed by the Trail Making Task will produce more differentiated network configurations or modular networks. Accordingly, we hypothesize that taking part in the Trail Making Test would produce a succession of distinct, modular networks of multiplicative interactions among movement-system components (Hypothesis 1.2).

Aim 1 approach network modeling from the vantage point of traditional modeling that these modular networks should be static. In Aim 2, we will relax this premise to investigate how the cascade-like interactivity exhibits a continuum of variability within so-called modular networks and could underwrite the transitions between separate network configurations. Specifically, we will investigate how shorter-timescale perturbations destabilizing the upright stance interact with the longer-timescale constraints on task completion to facilitate transitions among different network configurations. We base our predictions on recent findings of functional brain networks, which suggest that performing two tasks simultaneously or in close succession relies on the flexible reconfiguration of the brain networks (Alavash et al., 2015; Ekman et al., 2012; Hilgetag et al., 2001; Lam and Shin, 1998). Indeed, performance in different concurrent tasks benefits from unique functional brain networks at various timescales: integration of local, intermediate, or global networks (Alavash et al., 2015). Furthermore, the inability of the brain networks to sustain two separate topological configurations at once, each supporting the performance in one of the dual-task components, causes moment-to-moment fluctuations in the dual-task behavior (Alavash et al., 2016). Accordingly, we will examine the extent of modularity and the strength of connectivity between modular networks on multiplicative interactions as part of Aim 2.

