Multifractality refers to blending processes across different timescales, producing emergent structures. Multifractal spectrum width will be estimated using Chhabra and Jensens (1989) direct method. A non-zero width will indicate interactions in component processes producing rapidly changing periods of variability, such as small and large changes in fluctuations. To identify whether a nonzero width reflects multifractality due to nonlinearity, the multifractal spectral width for the original series will be compared to those for 32 Iterated Amplitude Adjusted Fourier Transform (IAAFT) surrogates (Ihlen, 2012; Schreiber and Schmitz, 1996). IAAFT randomizes original values time-symmetrically around the autoregressive structure, generating surrogates that randomize phase ordering of the original series spectral

amplitudes while preserving linear temporal correlations. The one-sample t-statistic takes the subtractive difference between the multifractal spectrum widths for the original series and 32 surrogates, dividing by the standard error of the spectrum width for the 32 surrogates. The greater the value of the t-statistic, the greater the multifractality in the original series due to nonlinear as opposed to linear sources.

Network modeling of multiplicative interactions

Vector autoregression (VAR) analysis will be used to model multiplicative interactions across the CoP, CoM, and 79 markers, represented in the model as (CoP, CoM, M1, M2, ..., M79). VAR captures interdependencies amongst concurrent series and will model the effects of t-statistic across anatomical locations in subsequent segments. VAR will yield a temporal trajectory of weights for each combination, defining a directional weighted musculoskeletal network for each participant and task condition. These functional networks will be transformed into binary networks to compare with the anatomical network.

Thresholding the weights using a single, unique threshold value corresponding to the percolation threshold (Esfahlani and Sayama, 2018) will yield a minimally connected network across task conditions. In this sparse network, each node will be connected to at least one node by an edge at one of the layers of the multiplex network.

Statistical analysis

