A full-factorial regression model will test the impulses and responses of each marker position. Impulse and Response will serve as class variables indicating the locations of impulse and response variables. Statistical significance will be interpreted as evidence of the flow of nonlinearities in movement fluctuations between the corresponding pair of anatomical locations, with the flow direction from the Impulse variable to the Response variable. Statistical significance will be set at a Type I error rate of 5%.

Extraction of functional musculoskeletal modules

The Louvain algorithm will extract functional musculoskeletal modules from the entire network. Consensus clustering will be implemented to achieve a stable partition (Lancichinetti and Fortunato, 2012). Multiplex modularity analysis will identify the functional musculoskeletal modules across different task conditions---MolTi software (<https://github.com/gilles-didier/MolTi>) will be utilized to identify functional musculoskeletal modules within multiplex networks by optimizing multiplex modularity through the modified Louvain algorithm.

Comparison of functional musculoskeletal networks across task conditions

The networks will be coarse-grained to compare functional musculoskeletal networks across task conditions (Kujala et al., 2016). The functional modules estimated across task conditions will coarse-grain the binary networks and then compare the strength of the inter-

and intra-module connections across task conditions. The nodes in clustered networks represent modules, and the edges signify the relationships between modules.

D. Does this study involve the collection of blood, urine, saliva or other human biological material (HBM)?

No

DRUGS, BIOLOGIC DRUGS AND DEVICES

13. Drugs and Biologic Drugs

1. Does this research involve the use of drugs or biologics?

No

14. Devices

1. Does this research involve a medical device(s) (including an in vitro device [IVD] (assay), and medical software)?

No

CONFIDENTIALITY AND PRIVACY

15. Confidentiality and Privacy

A. Describe where research data will be stored. Check all that apply.

[contact] (secure UNMC or UNO designated cloud-based storage site)

◆ Microsoft Office 365 application (including SharePoint, OneDrive for Business, Teams or Streams) (UNMC, UNO or NU system instance) (secure UNMC or UNO designated cloud-based storage site)

Other secure UNMC or UNO designated cloud-based storage site - describe:

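### The succession of networks predicted by Hypotheses 1.2 and 2.2 has no matching analysis, because networks are formed and compared only per participant and task condition

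*Protocol*

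**What the plan says.** The hypotheses stand in the Protocol, Section II, item 3 (Background and Rationale), and are repeated in the abstract (item 1).

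- Hypothesis 1.2 is that "taking part in the Trail Making Test would produce a succession of distinct, modular networks of multiplicative interactions among movement-system components (Hypothesis 1.2").
- Hypothesis 2.2 is that the same test on the balance board "would produce a succession of distinct, modular networks of multiplicative interactions with increased connectivity among these modules" relative to stable standing.
- Between the two, item 3 says that Aim 1 works "from the vantage point of traditional modeling that these modular networks should be static". Aim 2 is to relax that premise and look at transitions between configurations.

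The analysis stands in item 12.C. The VAR models effects from one segment to the next across 81 series (CoP, CoM and 79 markers). It is said to give, for each pair of series, weights that follow a course over time, "defining a directional weighted musculoskeletal network for each participant and task condition". One percolation threshold is then applied over the conditions, and the Louvain algorithm is run on the whole network. After that, "Multiplex modularity analysis will identify the functional musculoskeletal modules across different task conditions". Finally, the coarse-grained networks are compared between conditions on the strength of connections within and between modules.

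**The concern.** A succession is a statement about order in time: at least two networks, distinguishable from each other, one after the other within the task. The pipeline carries one network per participant and condition into every later step. If followed as written, it can show that the Trail Making network differs from the stance network. It can neither support nor refute the claim that the Trail Making Test runs through several networks.

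This matters most for Hypothesis 2.2. Apart from the task, Hypotheses 2.1 and 2.2 both predict modular networks with more connectivity between modules than in stable standing. What 2.2 adds is the succession, and that is the part without an analysis. The risk is that a static difference between conditions is read as evidence for a dynamic hypothesis.

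The background makes time central. It faults earlier network work for "preserving spatial or structural information while collapsing across time", and it presents cascade modelling as the remedy.

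**Working it through.** The plan gives no figure for this point, so there is none to reproduce. The check has two parts.

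**1. The dimension each step works on (item 12.C)**

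| Step | Works on | Within-trial sequence of networks? |
|---|---|---|
| VAR on segment-wise t-statistics | 81 series, segment to segment | Weights over time are mentioned; the resulting network is per participant and condition |
| Percolation threshold | all conditions together | No |
| Full-factorial impulse-response regression | pairs of locations | No; it concerns directed flow between locations |
| Louvain with consensus clustering | the whole network | No |
| Multiplex modularity | layers are task conditions | No |
| Coarse-grained comparison | between conditions | No |

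Count of networks as written:

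- Per participant: 4 conditions × 1 = 4.
- For 50 participants (item 4): 4 × 50 = 200.
- Per participant within one Trail Making condition: 1, against the 2 or more that a succession needs.

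The condition layers cannot stand in for a time axis. Item 12.A randomizes the order of the 12 trials for each participant, so conditions have no common order in time.

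**2. What a within-trial sequence would need**

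Inputs from the protocol: 2 + 79 = 81 nodes (12.C); trials of 7 to 8 minutes, that is 420 to 480 s (12.A); three trials per condition (12.A); recording at 200 Hz (12.A). Assumptions, because the protocol gives neither lag order nor segment length: an unrestricted lag-1 VAR with intercept, and each network fitted separately.

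- Lag coefficients: 81 × 81 = 6561.
- Parameters per equation: 81 + 1 = 82.
- Minimum segments per network: 82 + 1 (one residual degree of freedom) + 1 (lost to the lag) = 84.
- Longest possible segment for K networks in one trial: trial length / (84 × K).

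| K | 420 s trial | 480 s trial |
|---|---|---|
| 1 | 5.0 s | 5.7 s |
| 2 | 2.5 s | 2.9 s |
| 3 | 1.7 s | 1.9 s |
| 5 | 1.0 s | 1.1 s |

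Pooling matching windows over the three trials relaxes this. One segment is then lost per trial, so 83 + 3 = 86 segments are needed. For K = 2 the longest segment is 3 × 210 / 86 = 7.3 s to 3 × 240 / 86 = 8.4 s.

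These are bare minima for a fit to exist, not for a stable one. Each segment must also be long enough for a multifractal spectrum width and its comparison with 32 surrogates. At K = 2 without pooling, 2.5 s at 200 Hz is 500 samples.

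**The case against.** **The hypotheses remain testable.** A reader might infer that two of the four hypotheses cannot be tested at all. The protocol does not support that. Item 12.C extracts modules and compares connection strength within and between them by condition. Item 3 names the extent of modularity and the connectivity between modules as what Aim 2 will examine. This covers the modularity part of 1.2 and the modularity and connectivity parts of 2.2. The objection stands in full.

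**Time is already in the VAR.** Segment-to-segment effects and weights that follow a course over time could mean time-varying weights, or a response course over lags. The text does not settle which, so it would go too far to say that the plan discards time altogether. What remains is that the sentence ends in one network per participant and condition, and no later step turns the course into a sequence of networks.

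**The static premise need not contradict Hypothesis 1.2.** A reader might infer an outright contradiction within Aim 1. A sequence of internally static networks is a coherent reading, with Aim 2 then taking up the variability within them and the transitions between them. The sentence is unclear rather than shown to be wrong.

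**This is detail for a statistical analysis plan.** Item 12.C asks only for a brief description, and window lengths, transition criteria and null models may properly be set elsewhere. That stands for the detail. It does not dispose of the point, because the protocol itself states the network unit and the multiplex layers. A plan with windowed networks would have to depart from both.

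**Conclusion.** The point holds for the succession component only. Hypotheses 1.2 and 2.2 predict an ordered set of networks within the Trail Making Test, while the stated unit gives one network per participant in each Trail Making condition. No step forms successive networks, defines when two are distinct, or detects a transition. The other components of both hypotheses keep an analysis.

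This rests on reading the network unit in item 12.C as written. If the course of weights over time was meant to yield a network for each stretch of a trial, the protocol does not say so, and the later steps do not use it. The count of 84 segments rests on the assumed unrestricted lag-1 fit. It bears on how feasible the remedy is, not on whether the mismatch exists.

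Severity: should-fix. Data collection and sample size are not affected.

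**What to change.** Choose one of two routes before analysis.

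**(a) Analyse the succession.** For Hypotheses 1.2 and 2.2:

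- Estimate networks in consecutive windows within each trial, or per leg of the trail, using the laser trace that item 12.A already records. Stance has no legs, so it would need windows of matching length.
- Use the windows, nested in condition, as the multiplex layers. Module membership must be free to differ between windows; a partition shared by all layers could not show switching.
- Compare the rate at which nodes change module between the Trail Making Test and stance.
- Use two nulls: a stationary single-network null for distinctness, and shuffled window order for ordering.

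This needs no new data, but it is not light work. At 84 or more segments per network under the assumed fit, it would require shrinkage, fewer nodes or pooling over the three trials. Pooling assumes that transitions fall at similar times in each trial. If this proves infeasible, take route (b).

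**(b) Reword.** Remove the succession-and-distinctness wording from Hypotheses 1.2 and 2.2 in the abstract and in item 3. State both as static contrasts between conditions in modularity and between-module connectivity. Present the transitions mentioned for Aim 2 as motivation rather than as something tested. This costs a few words and gives up the dynamic claim; 2.2 would then differ from 2.1 only in the task.

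**Under either route,** say in item 3 whether static, for Aim 1, means one fixed network or a sequence of internally static networks.
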